Domain 4 (exploratory outcomes: HIV/PrEP linkage outcomes): (a) number of HIV+ youth referred to HIV treatment at 3, 6, and 12 months FUs, (b) number of HIV+ youth attending at least one treatment appointment at 3, 6, and 12 months FUs; (c) number of youth behaviorally PrEP eligible referred to PrEP/medical care at 3, 6, and 12 months FUs, (b) number of youth behaviorally PrEP eligible attending at least one HIV care appointment care at 3, 6, and 12 months FUs.

TRIAL MANAGEMENT

Study/data collection sites

Data will be collected at **Brooklyn Justice Initiative (BJI), run by Center for Court Innovation**. BJI is an alternative sentencing program (ASP) for JIY processed through Brooklyn Criminal Court. BJI aims to reduce re-offending and increase public safety; promote use of meaningful social services; provide rigorous compliance monitoring; and reduce criminal convictions and use of jail. Located in the Brooklyn Criminal Courthouse, BJI serves 9,000 youth/year; almost all (94%) are mandated to BJI for ≤ 15 days.

Study sample description

To address the study aims we will collect data from a sample of youth aged 18-24 who have been placed in BJI (sample 1), from a sample of HIV testing outreach staff (sample 2) and from staff at BJI (Sample 3).

Sample size and power

The total sample size of sample 1 will comprise N=472 youth currently enrolled at BJI: n=14 youth will serve on an advisory panel to provide feedback as MOVE and NYSBIRT are adapted; n=8 youth will pilot test the adapted Link2CARE protocols prior to the efficacy test of Link2CARE; and n=450 youth will be randomly assigned (1:1) to either Link2CARE or standard of care. Sample 2 will comprise N=2 Project STAY outreach workers who will be embedded at BJI and will deliver all elements of Link2CARE to youth. Sample 3 sample size is expected to be all 15 staff who work at BJI.

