Based on our previous work, the retention rate for studies of JYI was about 75% to 80%. Even though we anticipate being able to maintain 20% attrition, we conservatively use 25% attrition at 12-month FU in this power calculation. Under such assumptions and with a baseline sample of 450 participants, we estimate a final sample of at least n=338 with complete data for the primary analysis at 12-month FU. With 169 participants per group and the use of Bonferroni correction, we will be able to provide 80% power to detect a standardized effect size of .35 or more on any of the three primary outcomes (i.e., total number of unprotected anal and vaginal sex occasions in past three months, acceptance of HIV testing at initial offering; and frequency of substance use in past 30 days). The standardized effect size of .35 is considered as a relatively small to moderate effect size according to Cohen⁴ and our previous study suggests that it is an achievable effect. A substantial increase in sample size will not strongly impact effect size – e.g. to reduce the standardized effect size from .35 to .32, 100 more participants (22% increase in current sample size) would be required. Even if actual attrition is greater than expected e.g. say 30%, the detectable standardized effect size will only increase slightly to .36. Furthermore, as we will impute missing data using informative covariates for the primary analyses and using a less conservative Holm procedure for multiple comparison adjustment, power to detect such effects will actually be greater than 80%.

Table 1. Inclusion/exclusion criteria

Study Phase	Study Sample	Inclusion Criteria	Exclusion Criteria
Phase 1: Adaptation for Link2CARE	Peer advisory panel n=14	1) Between 18-24 years of age 2) Currently enrolled in BJI 3) Conversant in English (in the past two years, only two JIY at BJI have required language assistance).	1) Medical or psychiatric illness requiring hospitalization 2) Serious suicidal or homicidal ideation
	BJI staff n=6	1) Currently employed at BJI	None
Phase 2: Link2CARE Efficacy Trial and Implementation Evaluation	Pilot Youth n=8	1) Between 18-24 years of age 2) Currently enrolled in BJI 3) Conversant in English (in the past two years, only two JIY at BJI have required language assistance).	1) Medical or psychiatric illness requiring hospitalization 2) Serious suicidal or homicidal ideation

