
Analysis of participant attrition and missing data. We will make every effort to retain participants in the study to avoid bias due to attrition. For those individuals who refuse continued participation, we will document reasons for study discontinuation and Rubin's multiple imputation method with 11 repeated imputations will be

employed to impute the missing endpoint for conducting the intent-to-treat analysis.

QUALITY ASSURANCE

Procedures in place to ensure the validity and integrity of the data

All data collection protocols include a form on which research staff members record any problems with the data collection or unusual occurrences during the collection. They also are encouraged to bring problems to the attention of the Project Director, or PI. These members of the research staff also meet on a regular basis to identify and address any issues that arise. These procedures allow our research staff an opportunity to quickly review and respond to any possible concerns. We expect missing data to be minimal, nevertheless regular (quarterly) quality assurance checks will be made by the Project Director to identify any systematic missing information and remedies will be enacted.

Procedures to guarantee the accuracy and completeness of the data, during data collection, entry, transmission, and analysis.

To check for errors in data entry, we will adhere to the following protocol. All face-to-face surveys will be recorded. One out of every seven recordings for each interviewer will be compared to the entered interview. If we identify a proportion of errors that is more than 1% error, we will temporarily suspend the interviewer from active interviewing. We will listen to all interviews for comparison purposes, identifying any errors and will re-train the interviewer to ensure accuracy and completeness of all face-to-face survey interviews. A subset (10%) of all data from hard-copy/paper-pencil instruments that is entered into the project database will be similarly checked. If we identify a proportion of errors that is more than 1% error, we will reenter all questionnaires and subsequently compare both data sets. We will go back to the original surveys to resolve all inconsistencies. To prevent data entry problems we will prepare a data entry system that will alert us when data are entered that are out of range.

Procedures for preventing and addressing breaches of confidentiality

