Only two of the three co-primary endpoints will be monitored for early stopping: (1) total number of unprotected anal and vaginal sex occasions in past three months at 12 month FU; (2) any HIV testing between 6-month and 12-month FU (y/n). We will follow a modified Haybittle-Peto rule⁷ to propose early stopping as follows: the z-score for testing the null hypothesis for each of the two primary outcomes will be calculated once during interim analyses (see below) when one-quarter of the expected total 12-month outcome data has been observed (after approximately 6-months of 12-month data collection). This will allow the PSMB to recommend continuing to recruit subjects or stop the trial for strong positive or negative efficacy prior to the end of subject recruitment.

The z-score for early stopping will be $Z = 3.6623$ for either monitored outcome, corresponding to a normal two-tailed critical value cutting off nominal probability 0.00025 in each tail. It follows that either endpoint may suggest early stopping with total two-tailed probability 0.0005 under the null hypothesis and therefore the probability of early stopping under the null hypothesis for either endpoint in either direction will be no greater than 0.001. This stopping rule is less conservative than an O'Brien-Fleming-like alpha spending function monitoring plan, yet is still sufficiently conservative to leave the terminal significance criteria nearly unaffected. In particular, assuming no early stopping, if either of the two monitored co-primary endpoints specified above possesses the smallest P -value among all three co-primary endpoints, the group comparison will be declared significant at the 0.05 level (adjusted for multiple comparisons) if the terminal z-score criterion is $Z = 2.3978$ or greater. This Z -score is very close to the nominal $0.05/3 \approx 0.01667$ two-tailed normal critical value of 2.3940, which is the initial required criterion under the Holm step-down procedure without sequential monitoring. If the unmonitored co-primary endpoint (acceptance of HIV testing at initial offering, y/n) should have its P -value as smallest and less than or equal to $0.05/3 \approx 0.01667$, then it will be declared significant (at the two-tailed 0.05 level, adjusted for multiple comparisons).

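### With 11 imputations, a near-threshold result on either 12-month co-primary can depend on the random seed; at least 100 would cut this about threefold at the cost of computing time only

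*Combined protocol and SAP*

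**What the plan says.** The paragraph on attrition and missing data, at the end of the data analysis plan, states that Rubin's "multiple imputation method with 11 repeated imputations will be" "employed to impute the missing endpoint for conducting the intent-to-treat analysis". It introduces this with the words "For those individuals who refuse continued participation, we will document reasons for study discontinuation".

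The section on sample size and power confirms that imputation feeds the main tests: "as we will impute missing data using informative covariates for the primary analyses". On the amount of missing data it says "we conservatively use 25% attrition at 12-month FU in this power calculation", and it also considers 30%.

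The section on trial stopping rules sets the final decision. A monitored co-primary with the smallest p-value must reach Z = 2.3978. The same section gives the unmonitored value as the "two-tailed normal critical value of 2.3940, which is the initial required criterion under the Holm step-down procedure without sequential monitoring". The later Holm steps use 0.025 and 0.05, and failure at one step ends testing.

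The documents give no seed, no limit on Monte Carlo error, no reason for choosing 11, and no fraction of missing information.

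**The concern.** Multiple imputation draws random values, so the pooled z depends on the seed as well as on the data. The usual defence of a small number of imputations is efficiency. With a fraction of missing information (FMI) of 0.25, 11 imputations are 1/(1 + 0.25/11) = 98% efficient relative to infinitely many. That figure describes the variance of the estimate over repeated trials. It does not say whether two analysts who follow the plan on the same locked data would get the same p-value.

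With 11 imputations they may not, if the result lies near a threshold. Because Holm testing stops at the first failure, a change at one step can also decide whether the remaining co-primaries are tested at all.

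**Working it through.** **Inputs from the documents.** 450 randomised 1:1, so 225 per arm; 25% attrition (30% as the worse case); 169 completers per arm; standardized effect 0.35; 80% power; two-sided 0.05/3 at the first step; Z = 2.3978 for monitored endpoints; m = 11.

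**Assumptions.** FMI (λ) of 0.10 to 0.30, anchored on the 25% and 30% attrition figures, and a normal outcome as a proxy for the count and binary endpoints.

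**1. The plan's own figures.** The two-sided normal critical value at 0.05/3 is 2.3940, as stated. With 169 per arm the expected z is 0.35 × √(169/2) = 3.217, and power is Φ(3.217 − 2.394) = 79.5%, against 80% stated. The value 2.3978 is reproduced with one look at 25% information and a boundary of 3.6623.

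**2. Noise in z at fixed data.** Scale the total variance at infinite m to 1, so that the between-imputation variance is λ. Over seeds, the pooled estimate has variance λ/m, and the estimated between-imputation variance has relative standard deviation √(2/(m−1)). Hence

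SD(z) ≈ √{ λ/m + [ (z/2) · λ · √(2/(m−1)) ]² }.

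For λ = 0.25, m = 11, z = 2.3978:
- first term: 0.25/11 = 0.0227
- second term: (1.199 × 0.25 × 0.447)² = 0.134² = 0.0180
- SD = √0.0407 = 0.20

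The shorter formula √(λ/m) gives 0.15. It is too low because it leaves out the noise in the variance estimate.

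**3. Range over FMI.** The SDs were checked by random draws under Rubin's rules. The disagreement columns give the share of trials in which two seeds fall on opposite sides of the first threshold, averaged over results under the design alternative.

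| FMI (assumed) | SD of z, m = 11 | SD of z, m = 100 | Disagree, m = 11 | Disagree, m = 100 |
|---|---|---|---|---|
| 0.10 | 0.11 | 0.036 | 3.6% | 1.1% |
| 0.15 | 0.14 | 0.047 | 4.6% | 1.5% |
| 0.20 | 0.17 | 0.056 | 5.7% | 1.8% |
| 0.25 | 0.20 | 0.066 | 6.7% | 2.1% |
| 0.30 | 0.23 | 0.075 | 7.7% | 2.4% |

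Under the null, two seeds disagree in 0.6% to 1.2% of trials at m = 11.

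**4. At the boundary.** Take FMI 0.25 and an infinite-imputation z of 2.3978. With m = 11, about 47% of seeds pass. The 5th to 95th percentile of p over seeds is about 0.007 to 0.044 with Rubin's t reference (upper end 0.040 with the normal), which spans both 0.0167 and 0.025. With m = 100 it is about 0.012 to 0.022.

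**5. Away from the boundary.** At FMI 0.25 and m = 11, the chance that two seeds disagree is 24% at z = 2.2, 50% at 2.40, 31% at 2.6 and 7.5% at 2.8.

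**6. Full simulation.** 225 per arm, 56 missing per arm, normal outcome, imputation within arm:

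| Covariate correlation | FMI | SD of z near the cut-off | Disagree |
|---|---|---|---|
| none | 0.26 | 0.22 | 8% |
| 0.5 | 0.21 | 0.17 | 6% |
| 0.7 | 0.16 | 0.14 | 3% |

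**7. Validity.** Type I error at m = 11 against the normal cut-off is about 0.017 to 0.018, against 0.0167.

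**The case against.** The strongest reply is that nothing is invalid. Type I error is almost unchanged, efficiency is about 98%, and the documents contain nothing that contradicts 11 imputations. All of that stands.

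The scope is also narrow. Acceptance of HIV testing is recorded at the initial offer, so only two of the three co-primaries are exposed. The power section expects 20% attrition and calls 25% conservative. The missing-data paragraph speaks of participants who refuse to continue, who may be fewer than all those lost. Strong covariates would lower the FMI further. These points reduce the size but do not remove it: at FMI 0.05 the SD at m = 11 is still about 0.07.

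A reader might infer that, because the plan distinguishes 2.3978 from 2.3940, z should be reproducible to that precision. The documents do not support this. The difference is the small alpha adjustment for one interim look, and the stopping-rules section itself calls the two values very close. It is not a precision target, and 100 imputations would not meet it either.

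A reader might also infer that the primary conclusion is unstable in general. It is not: under the design alternative, more than 92% of trials give the same first-threshold decision from two seeds even at FMI 0.30 (100% − 7.7% = 92.3%).

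Finally, a fixed seed makes a run repeatable without reducing its noise. That is correct, and it is why the number of imputations must change first.

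**Conclusion.** The point holds as a modest matter of reproducibility. With 11 imputations, the seed alone moves z by an SD of about 0.11 to 0.23 near the cut-off, and it would change the first-threshold decision between two runs in about 3.6% to 7.7% of trials under the design alternative. With 100 imputations the SD is about 0.04 to 0.08 and the disagreement about 1.1% to 2.4%, so roughly 2.5 to 5 percentage points of seed dependence are removed.

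It concerns only unprotected sex occasions at 12 months and HIV testing between 6 and 12 months, and only results near a threshold. The sizes rest on the assumed FMI range and the normal proxy. There is no evidence of bias or of inflated type I error.

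**What to change.** In the paragraph on attrition and missing data, replace 11 with at least 100 imputations, state that the seed is fixed before unblinding, and require the Monte Carlo error of the pooled z to be reported with each imputed co-primary result. The figure of 100 is a judgement and not a threshold taken from the documents; the reported Monte Carlo error will show whether it was enough for the result obtained.

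Rubin's t reference may be stated as well, but it is secondary. At FMI 0.25 the degrees of freedom are (m − 1)/λ² = 10/0.0625 = 160 with 11 imputations (first-step critical value 2.419 against 2.394) and 99/0.0625 = 1,584 with 100, where the t and normal values almost coincide.

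The cost is computing time only. Sample size, data collection and the Holm thresholds are unchanged.
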